6.4.4. Laboratory parameters

Not applicable.

6.4.5. Vital signs/Physical examination

Vital Signs

Measurement of vital signs will include body temperature (°C), systolic and diastolic blood pressure (mmHg), heart rate (beats/min), respiratory rate (beats/min).

Measurements of blood pressure will be carried out after at least 5 minutes resting in the supine position and always on the same arm. In case of any suspicion of unreliable measurement, blood pressure will be measured again and the value obtained the second time will be considered as definitive.

Vital signs will be summarized at each timepoint as well as absolute changes from baseline.

In advance, the proportion on patients by overall evaluation (i.e., Normal, Abnormal and not clinically significant and Abnormal and clinically significant) will be provided at each timepoint.

In order to display the number of patients with potentially clinically significant vital signs at screening vs post-screening timepoint, shift tables will be produced.

Physical examination

A complete physical examination will be performed at screening and Visit 4 and should include assessments of the cardiovascular, respiratory, gastrointestinal, and neurological systems. Height and weight will also be measured and recorded to

	
Statistical Analysis Plan

	
Sponsor: ALMIRALL, S.A.

	
Protocol number: M-14789-42

allow calculation of body mass index (BMI). For this, patients should be in light indoor clothes without shoes.

Summary descriptions of weight, height and BMI will be provided as well as the proportions of patients according to the reported results and the clinically relevance of the following assessments: General appearance, Eyes, ears, nose and throat, Cardiovascular, Respiratory, Gastrointestinal, Urogenital, Neurological, Musculoskeletal, Lymph nodes, Dermatology and in case Other assessments at each timepoint.

In order to display the number of patients with potentially clinically significant results (i.e., Normal, Abnormal and not clinically significant and Abnormal and clinically significant) at screening vs Final visit, shift table will be produced.

6.4.6. Other safety parameters

Local tolerability signs and Local skin reaction.

Local tolerability signs (LTSs) and local skin reactions (LSRs) will be assessed at Day 57, based on the Investigator's review of the following signs in the treatment field: Erythema/redness, Flaking/scaling, Crusting/scabs, Swelling, Vesiculation/pustulation and Erosion/ulceration.

The signs will be evaluated at each scheduled site-visit both individually and as a composite score (total of the 6 individual scores).

These signs will be assessed using a 4-point grading scale, composed as follows:

- 0=absent;
- 1=mild (slightly, barely perceptible);
- 2=moderate (distinct presence);
- 3=severe (marked, intense).

Only signs (LTSs and LSRs together) evaluated at Baseline, Visit 3 (Day 8), Visit 4 (Day 57) by the Investigators (i.e., collected in LOCAL SKIN REACTION or LOCAL TOLERABILITY SIGNS eCRF pages) will be summarized by country and overall reporting the following information:

- Number of patients at each visit;
- Frequency of patients who provided information on signs at each visit (calculated on patients who performed the visit);
- Frequency of patients who did not provide information on signs at each visit (calculated on patients who performed the visit);
- Frequency of patients with at least one sign of at least Mild severity (calculated on patient who performed the visit and on patients with information on sign at visit);

	Statistical Analysis Plan Sponsor: ALMIRALL, S.A. Protocol number: M-14789-42
---	--

- For each of the six signs (erythema, flaking/scaling, crusting, swelling, vesiculation/pustulation, and erosion/ulceration at the application-site) the number and percentage (on patients with information on sign at visit) of patients corresponding to each evaluated sign;
- A composite score will be calculated and summarized as the sum of the scores for all six signs (range 0 to 18, with higher scores indicating more severe reactions) at each visit.

Signs reported by patients (i.e., collected in LOCAL SKIN REACTIONS/LOCAL TOLERABILITY SIGNS REPORTED BY PATIENT eCRF page) will be summarized by country and overall. The proportion of patients with at least one sign as well as the number of signs reported by each patient will be described.

Moreover, all local tolerability signs and local skin reactions will be listed in Section 16.

Pregnancy

Considering female patients, at screening and baseline visit a urine pregnancy test should be performed for all women of childbearing potential.

Moreover, women who reported positive urine pregnancy test will perform an additional serum pregnancy test for confirmation.

Pregnancy test results will be listed only.

Other

Information about kit assignment, Instructions for self-administration, patient diary and return of patient diary will be listed.

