10.5.4 LSR Assessments

After the assessment of AEs at the scheduled visits as mentioned in **Table 1**, the Investigator or Sub investigator will assess for LSRs in the treatment area.

LSR signs on the treatment area at the application-site include the following:

- erythema/redness
- flaking/scaling
- crusting/scabs
- swelling
- vesiculation/pustulation
- erosion/ulceration

These signs will be assessed using a 4-point grading scale; 0=absent, 1=mild (slightly, barely perceptible), 2=moderate (distinct presence), and 3=severe (marked, intense).

Application-site reactions such as application-site pruritus and application-site pain (including pain, tenderness, stinging, and burning sensation) not classified as LSRs will be reported as adverse events (AE). LSRs will be reported separately from AEs. The same Investigator or Sub investigator will conduct the LSR assessment at all visits for an individual subject.

All application site reactions and LSRs will be followed to resolution, or if resolution is unlikely, to stabilization. Treatment for any LSR and other application site reactions will be recorded on the Concomitant Medications eCRF. Interruption/discontinuation of study treatment for an LSR will be recorded on the eCRF.

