11.4.1 Analysis of Safety and Tolerability Endpoints

The analyses of safety and tolerability outcomes will be performed on the Safety Population. Safety outcomes include adverse events, blood pressure and heart rate (vital signs).

LSRs

LSRs assessment results obtained through Day 57 will be summarized by visit reporting for each of the six signs (erythema, flaking/scaling, crusting, swelling, vesiculation/pustulation, and erosion/ulceration at the application-site) the number and percentage of patients corresponding to each of the score ranging from 0=absent to 3=severe. In addition, a composite score will be calculated as the sum of the scores for all six signs (range 0 to 18, with higher scores indicating more severe reactions) at each visit for each patient and summarized with standard summary statistics for continuous variables.

Application-site reactions such as application-site pruritus or application-site pain (including pain, tenderness, stinging, and burning sensation) not classified as LSRs will be reported as adverse events (AE)..

Adverse Events

The incidence of AEs, SAEs and AESI recorded throughout the study will be summarized by MedDRA SOC and PT. A summary of AEs by SOC, PT and severity will be also provided. All related AEs, SAEs, AEs with an outcome of death, AEs leading to treatment discontinuation will be summarized by MedDRA SOC and PT. Deaths will be listed together with all relevant information.

The frequency of comorbidities will be analyzed descriptively.

Vital Signs

Vital signs (blood pressure and heart rate) will be summarized at each time point and as change from screening value with descriptive statistics.

Medication Adherence

Medication adherence assessed with patient-kept diary will be summarized with frequency distribution from Day 0 to Day 4

11.4.2

Analysis of Pharmacokinetic Parameters

Not applicable

11.4.3

Pharmacokinetic/Pharmacodynamic Analysis

Not applicable

11.5

Handling of Missing Data

In case of missing values, no imputation will be done. Further details on the handling of missing data will be provided in the SAP.

11.6

Multiplicity Strategy

No statistical test will be conducted, so there is no need to consider multiplicity issue.

11.7

Interim Analysis

An intermediate descriptive analysis is planned when 50% of patients have completed the study. Further details will be provided in the SAP.

12 Data Handling, Processing, and Record Keeping

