3.4. Schedule of Time and Events

The flowchart of the follow-up visits and assessments scheduled for study centers is reported in Table 1 below.

Period	Screening ^a	Treatment					Follow-up			Final visit
		Baseline	-	-	-	-	Additional Visits * (Applicable for one site: Hospital Clinic de Barcelona)	AV1	AV2	
Visit	1	2					3			4
Days	-28 to -1	0	1	2	3	4	8	15	29	57
Visit time window (days)	± 3	± 3	-				± 3	± 3	± 3	± 3
Informed consent	X									
Inclusion & exclusion criteria	X									
Socio-demographic characteristics	X									
AK therapy history ^b	X									
Identification of treatment area ^c	X	X ^d								
Medical history	X									

	Statistical Analysis Plan									
	Sponsor: ALMIRALL, S.A. Protocol number: M-14789-42									

Period	Screening ^a	Treatment					Follow-up			Final visit
		Baseline	-	-	-	-	3	Additional Visits *		
Visit	1	2						AV1	AV2	4
Days	-28 to -1	0	1	2	3	4	8	15	29	57
Prior and concomitant medications/therapies	X	X ^d	X	X	X	X	X	X	X	X
Physical Examination	X									X
Vital signs	X						X			X
Skindex-16		X ^d								X
Organoleptic properties (Likert scale)							X			
TSQM-9										X
TSQM 1.4										X
AK lesion count	X	X ^d								X
Standardized Photography		X ^d					X			X
Olsen grading		X ^d								X
LC-OCT of clinical and subclinical lesions ^f		X ^d					X	X	X	X
EPQ ^g										X
AEs/SAEs ^e		X ^d	X	X	X	X	X	X	X	X
Local Tolerability Signs		X ^d	X	X	X	X	X	X	X	X
Pregnancy test for WOCBP ^h	X	X ^d								
Tirbanibulin (Study drug) application		X	X	X	X	X				
Patient Diary		X	X	X	X	X				

	<h2 style="text-align: center;">Statistical Analysis Plan</h2>								
	Sponsor: ALMIRALL, S.A. Protocol number: M-14789-42								

Period	Screening ^a	Treatment					Follow-up			
		Baseline		-	-	-	-	Additional Visits *	Final visit	
Visit	1	2	3	4	8	15	AV1	AV2		
Days	-28 to -1	0	1	2	3	4	8	15	29	57
Return of Study drug sachets (used and unused) and patient diary						X				

Note: The duration of time window planned for this study is +/- 3 days

Abbreviations: TSQM=Treatment Satisfaction Questionnaire for Medication; LC-OCT = Line-field Confocal Optical Coherence Tomography; EPQ=Expert Panel Questionnaire; AK=Actinic Keratoses; AE=Adverse Event; SAE=Serious Adverse Event; WOCBP=Women of Childbearing Potential;

* Additional visits 1 and 2 (AV1 and AV2) will be performed only in one clinical site: Hospital Clinic de Barcelona

- a. The duration for screening is 1 month.

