- b. This includes history of treatments namely topical medications freezing, laser, scraping, etc.
- c. The location and shape of the treatment area will be marked on an acetate transparency sheet or captured through standardized photography that will be kept for recording purposes. The treatment area will be also outlined with dots and dashes with an indelible marker on the patient' skin, to help him/her with daily self-administration of study ointment.
- d. These are baseline procedures/assessments and will be performed before application of study medication.
- e. AEs and local tolerability signs will be reported separately. At each study visit, AEs will be recorded before assessment of local tolerability signs in the treatment area. From Day 0 to Day 4, AEs and local tolerability signs will be recorded using patient diary. During rest of the study period, AEs and local tolerability signs will recorded and evaluated by the investigator at each visit or through telephonic follow-up in case of urgency.
- f. LC-OCT assessments are applicable only for one site: Hospital Clinic de Barcelona. LC-OCT assessment will be done for 2 lesions, which includes 1 clinical lesion and 1 subclinical lesion. eCRF will collect only the information about LC-OCT performed or not at each scheduled visit.
- g. EPQ comprises of 2 versions: patient version and clinician version. Patient version of the EPQ should be completed by the patient and clinician version by the clinicians.
- h. Initially, urine pregnancy test will be performed. If pregnancy is tested positive, serum pregnancy test will be performed for confirmation.

The total duration of each patient's participation in the trial is estimated to be 3 months, including 1 month for screening and 2 months for treatment, and follow-up.

- **Screening period** (period between Informed Consent Form (ICF) signature day, that could occur up to 28 days before to Day 0, and Day 0): before patient's signing the ICF, Investigators will describe in detail to the patient all activities and requirements,

	<h2 style="text-align: center;">Statistical Analysis Plan</h2> 
Sponsor: ALMIRALL, S.A.
 
Protocol number: M-14789-42

---	--

in order to ensure their understanding and compliance with sample collection and clinical examinations.

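### SAP 6.4.6 leaves one site's scheduled Day 15 and Day 29 skin-reaction grades out of every summary table, and no table gives patient-level incidence of investigator-graded signs across post-dose visits

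*SAP*

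**What the plan says.** SAP 6.4.6 makes three statements about timing. Its opening sentence places the assessment at Day 57. It then says "The signs will be evaluated at each scheduled site-visit both individually and as a composite score". The rule that governs the output is narrower: "Only signs (LTSs and LSRs together) evaluated at Baseline, Visit 3 (Day 8), Visit 4 (Day 57) by the Investigators" are to be summarised. That summary holds the frequency of patients with at least one sign at each visit, the breakdown for each of the six signs, and the composite score (0 to 18). All signs are also to be listed.

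The schedule in SAP 3.4 marks local tolerability signs at AV1 (Day 15) and AV2 (Day 29) as well, and its note says "Additional visits 1 and 2 (AV1 and AV2) will be performed only in one clinical site: Hospital Clinic de Barcelona". Footnote e to the schedule says "AEs and local tolerability signs will recorded and evaluated by the investigator at each visit or through telephonic follow-up in case of urgency".

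The supplied protocol (version 1.0) marks the signs at the same two additional visits in Table 1. Its section 11.4.1 has no visit restriction: "LSRs assessment results obtained through Day 57 will be summarized by visit reporting for each of the six signs", followed by the composite at each visit. Section 6 defines the safety endpoint as the incidence and severity of local skin reactions. SAP section 2 names the proportion of patients with at least one local tolerability sign as the endpoint, and lists physician-assessed severity and the composite score among its variables.

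**The concern.** Protocol 5.2 names local skin reactions as the primary safety concern with tirbanibulin. A rule that excludes scheduled grades of that risk from the summary needs a reason, and the SAP gives none.

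Two things are at stake. First, protocol 10.5.4 requires reactions to be followed until they resolve or stabilise. Day 15 and Day 29 are the only scheduled investigator gradings between Day 8 and Day 57, so they are the only scheduled data on how long reactions last, and no table shows them. Second, a set of by-visit tables describes prevalence at each visit. It does not answer the question the endpoint asks: how many patients had a given sign after treatment, and how severe it became.

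**Working it through.** **1. Where a Day 15 or Day 29 grade can appear**

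| Planned output | Contains these grades? |
|---|---|
| By-visit summary of investigator-assessed signs and composite (SAP 6.4.6) | No, restricted to Baseline, Day 8 and Day 57 |
| Summary of signs reported by patients (SAP 6.4.6) | No, a different source, and it gives occurrence and number of signs without severity |
| Adverse event tables by severity (SAP 6.4.3) | No, protocol 10.5.4 keeps local skin reactions separate from adverse events |
| Listing of all signs (SAP 6.4.6) | Yes |

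The grades are therefore reported, but not summarised.

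**2. How many patients this touches**

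Inputs: about 420 patients and at least 10 per site (SAP 3.1). The documents give three site totals: 35 + 7 = 42 (protocol synopsis and 7.1), 33 + 7 = 40 (SAP 4.6) and 30 + 7 = 37 (SAP 3.1). Barcelona's enrolment is not stated. Its lower bound is the minimum of 10. Its upper bound assumes that every other site enrols exactly 10: 420 − 10 × (sites − 1).

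- 42 sites: 420 − 410 = 10 patients (2.4%)
- 40 sites: 420 − 390 = 30 patients (7.1%)
- 37 sites: 420 − 360 = 60 patients (14.3%)

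With full attendance, each patient contributes two scheduled post-baseline gradings (Day 8, Day 57), and each Barcelona patient two more. The share left out of the tables is 2b / (840 + 2b) for b Barcelona patients:

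- b = 10: 20 / 860 = 2.3%
- b = 30: 60 / 900 = 6.7%
- b = 60: 120 / 960 = 12.5%

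Within Barcelona it is 2 of 4 scheduled post-baseline gradings. At every other site it is none, because Day 8 and Day 57 are the only scheduled post-baseline visits and both are tabulated.

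**3. What the by-visit tables can say about incidence**

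Take one sign at one severity threshold. Let p8 and p57 be the proportions of the same patients who meet it at Day 8 and at Day 57. The proportion who meet it at either visit lies between max(p8, p57) and min(1, p8 + p57). Where it falls depends on whether the same patients are affected at both visits, and the by-visit tables do not show that. The row for at least one sign of mild or greater severity does not help, because it too is computed visit by visit. The patient-level quantity exists only for patient-reported signs, which carry no grade. This gap applies to all 420 patients.

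**The case against.** The strongest reply is that little is lost. The omission concerns one site, probably a small number of patients, and a listing is a workable format for that. Protocol 11.4.1 asks for a summary by visit and not for a worst grade. A maximum over all assessments would also mix patients graded four times after dosing with patients graded twice. The point about reach stands and sets the size of this finding. The point about unequal assessment also stands, and the fix allows for it. Neither explains why the section contradicts its own statement about every scheduled site visit, or supplies a patient-level summary of the endpoint.

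Four stronger readings are tempting, and the documents do not support them.

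- A reader might infer that graded reactions from urgent contacts are being dropped. Footnote e provides for telephone recording, but protocol 10.5.4 ties the investigator's assessment of local skin reactions to scheduled visits ("After the assessment of AEs at the scheduled visits as mentioned in" Table 1). No text provides for a 0 to 3 grade by telephone.
- A reader might count Days 12 to 53, the 42 days between the Day 8 window (Days 5 to 11) and the Day 57 window (Days 54 to 60), as lost through this rule. That gap comes mostly from the visit schedule. The two additional visits, with their ±3 day windows, cover Days 12 to 18 and 26 to 32: 14 of the 42 days, at one site.
- A reader might infer that severe reactions are likely to be hidden. Protocol 5.1.4 reports that the commonest reactions in the phase 1 study, on the forearm, peaked around Days 5 to 10. The Day 8 window contains that interval. The loss is mainly about persistence and resolution.
- A reader might call this an undeclared departure from the protocol, since SAP 1.1 lists only a clarification on LC-OCT. The SAP refers to protocol versions 3.0 (Spain) and 2.0 (Italy), and the supplied protocol is version 1.0, so this cannot be confirmed.

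**Conclusion.** The point holds as a modest, inexpensive improvement. The inconsistency lies within the SAP and does not depend on which protocol version governs: the schedule requires signs at Day 15 and Day 29, section 6.4.6 says they are evaluated at each scheduled site visit, and the summary rule then excludes those two visits. The exclusion affects 10 patients at the stated minimum and up to 60 under the extreme assumption that all other sites (37 in total) enrol exactly 10. That is 2.3% to 12.5% of scheduled post-baseline gradings if attendance is complete. The excluded grades are listed, so they are not lost.

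The absence of a patient-level post-dose summary of investigator-graded signs is separate and applies at every site. It matters because the endpoint is stated as incidence and severity, and by-visit prevalence only bounds incidence.

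**What to change.** In SAP 6.4.6:

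1. Delete the word that restricts the summary to three visits, and align the opening sentence on timing with the schedule.
2. Add by-visit summaries at Day 15 and Day 29 for Hospital Clinic de Barcelona, labelled as one site.
3. Add a table of the worst post-dose investigator grade for each sign, and the worst composite score per patient. Base the main version on Day 8 and Day 57, the visits common to all sites, so that every patient has the same number of scheduled assessments.
4. Show a second version that uses all recorded investigator grades, including Day 15 and Day 29 and any unscheduled grade if one was recorded. Add a footnote that the number of assessments differs between patients.
5. State in one sentence how signs recorded by telephone or at unscheduled contacts are handled.

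No new data collection is needed. The cost is a few sentences and one or two extra tables. The downside is that the reported incidence may be slightly higher, because a patient counts if affected at any included post-dose visit.

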5.1 Background Information

5.1.1 Indication

Actinic keratoses interchangeably referred to as solar keratoses are common skin lesions primarily caused by non-ionizing radiation, in particular ultraviolet light associated with chronic sun exposure. The clinical manifestations are red, irregular, scaly plaques, or papules on the sun exposed areas, usually found on the face, balding scalp, cleavage, ears, lips. If left untreated, the lesions are associated with the risk of malignant transformation in non-melanoma skin cancer, including squamous cell carcinoma (SCC).² The risk of AK progression rate to invasive cutaneous SCC is estimated to be 0.25% to 1% each year. However, the causative factor of nearly 60% of SCC develops from AK.³ The presence of AK lesions in photo-exposed areas, such as the face and scalp, is relatively frequent among the Spanish population and constitutes one of the main reasons for consulting a dermatologist.² In fact, AK prevalence is observed to increase with age for both sexes, reaching 60.4% of patients older than 80.²

The mainline of AK treatment modalities includes cryosurgery, skin field therapy (topical agents like 5-fluorouracil, imiquimod, diclofenac) and photodynamic therapy. Relatively, these therapies demanded a long treatment period of approximately 4-16 weeks and were associated with numerous local skin reactions (LSR) like irritations, pain, ulcerations, erosions, pigmentations and scarring of the skin. These unmet factors increased the chance of low treatment compliance and undermine treatment success.^{4,5} The novel microtubule inhibitor tirbanibulin, its short treatment time (5 days) and minimal adverse reactions could address the unmet need of patients suffering from AK lesions, thereby increasing medication adherence and success.⁶

In this study, the impact of tirbanibulin on the wellbeing of patients will be evaluated in patients with a diagnosis of AK of the face or scalp following treatment with tirbanibulin ointment 1% administered once daily for 5 consecutive days. The study will mainly focus on treatment satisfaction.

5.1.2**Mechanism of Action**

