5.1.4 Clinical Studies

Till date, 4 clinical studies (one phase 1, one phase 2, and 2 phase 3) have been conducted to evaluate the efficacy and safety of tirbanibulin ointment 1% in subjects with AK. Details of the 4 studies are available in the Tirbanibulin ointment SmPC.

KX01-AK-01-US Study, a Phase 1, safety, tolerability, and pharmacokinetic study, demonstrated that tirbanibulin ointment 1% had good tolerance and showed favorable clinical performance in 30 adults with AK manifesting on dorsal forearm when administered at 50 or 200 mg daily over 3 or 5 consecutive days in an area of 25 or 100 cm². Mild to moderate and transient LSRs were observed in the majority of the subjects. The LSRs observed in greater percentage were erythema and flaking/scaling that peaked around Day 5-10, before returning to or close to baseline. Symptoms of pruritus, stinging, and burning at the treatment area were generally mild and transient. There were no serious adverse events (SAEs) or deaths, and no subjects discontinued due to an AE.

KX01-AK-002 Study, a Phase 2a, open-label, sequential group study, evaluated the efficacy and safety of tirbanibulin ointment 1% when applied daily in a treatment area of 25 cm² for 3 consecutive days (n=84 subjects) or 5 consecutive days (n=84 subjects) in adults with AK on face or scalp.

Thirty-six of 84 subjects (43%) in the 5-day regimen and 27 of 84 subjects (32%) in the 3-day regimen had 100% clearance of AK lesions in the treatment area on Day 57.

Clinical Trial **M-14789-42**

Clinical Trial Protocol Version No.1.0, Date 08/05/2022

Preliminary data showed that most of the 168 subjects treated had mild to moderate LSRs (primarily erythema and flaking/scaling. Eleven (6.5%) subjects had 16 treatment-emergent adverse events (TEAEs) considered treatment-related by the Investigator. Eight of these subjects had mild application-site reactions including pruritus, tenderness, or stinging. The remaining AEs considered by the Investigator to be treatment-related were mild headache, mild to moderate dizziness, mild arthralgia, or mild darkening of hair color near the treatment area. All treatment-related TEAEs resolved prior to or stabilized by Day 57. Four subjects reported 5 treatment-emergent SAEs. All SAEs were considered unrelated to study drug. No subject discontinued treatment due to AEs.

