
To evaluate efficacy outcomes of patients following treatment with Tirbanibulin ointment 1% administered once daily for 5 consecutive days.
	
 • Lesion clearance. • Number of lesions. 
 • Lesion clearance. • Number of lesions. 
 • Total AK lesion count. • New AK lesion count. • Old AK lesion count. 
Olsen characterization.
	
Proportion of patients with complete (100%) clearance of all lesions within the application area with 95% confidence interval.
 
Proportion of patients with partial (>75%) clearance of all lesions within the application area with 95% confidence interval.
 
Number of new and old AK lesions with 95% confidence interval.
 
Proportion of patients by Olsen characterization with 95% confidence interval.

	Statistical Analysis Plan Sponsor: ALMIRALL, S.A. Protocol number: M-14789-42
---	--

OBJECTIVES	VARIABLES	ENDPOINTS

To evaluate safety outcomes of patients following treatment with Tirbanibulin ointment 1% administered once daily for 5 consecutive days.
	
LC-OCT data of clinical and subclinical lesions.
 
 • Adverse events maximum severity grade. • Adverse events SOC. • Adverse events PT. • LTS composite score. • LTS severity grade assessed by physicians. • Number of LTS reported reported by patients. 	
LC-OCT of clinical and subclinical lesions as Atypia scores.
 
Proportion of patients reported at least one adverse event by incidence and severity.
 
Proportion of patients reported at least one local tolerability sign (LTS).

To evaluate medication adherence of patients following treatment with Tirbanibulin ointment 1% administered once daily for 5 consecutive days.
	
Number of missing doses applied.
	
Proportion of patients applying Tirbanibulin doses.

Exploratory objective(s): NA	NA	Exploratory endpoint(s): NA

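### Local skin signs are tabulated visit by visit with no within-patient comparison to the pre-dose grade, so new or worsened signs cannot be separated from pre-existing or residual AK

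*SAP*

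**What the plan says.** The SAP section 2 endpoint is the "Proportion of patients reported at least one local tolerability sign (LTS", with no reference to the patient's state before dosing. SAP 6.4.6 carries it out by visit: "Only signs (LTSs and LSRs together) evaluated at Baseline, Visit 3 (Day 8), Visit 4 (Day 57) by the Investigators" are summarized. At each visit it gives the "Frequency of patients with at least one sign of at least Mild severity" and the frequencies for each of six signs, and "A composite score will be calculated and summarized as the sum of the scores for all six signs". The threshold is the lowest non-zero grade, "1=mild (slightly, barely perceptible".

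Protocol 11.4.1 has the same structure: grade frequencies per sign by visit, and "a composite score will be calculated as the sum of the scores for all six signs" at each visit. Neither document defines a new or worsened sign, plans a shift table, or asks for change from Day 0 in a sign or in the composite.

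The reference value exists. The schedules in Protocol Table 1 and SAP 3.4 both mark the Day 0 assessment of the signs as pre-dose. Protocol 10.5.4 asks for the same assessor at every visit for a given patient.

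**The concern.** Two of the six graded signs, redness and scaling, are also how the protocol describes the disease: "The clinical manifestations are red, irregular, scaly plaques, or papules on the sun exposed areas". Inclusion criterion 3 puts 4-8 lesions inside the field that is graded. Nothing in Protocol 10.5.4 or SAP 6.4.6 tells the assessor whether lesional redness or scale is to be left out of the grade. SAP 3.3.3 confirms that there is no control treatment, so the patient's own Day 0 grade is the only available reference.

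Protocol 5.2 names these reactions as the primary safety concern and describes them as arising after application. The Protocol section 6 endpoint is their incidence and severity. A visit prevalence that can include signs present before the first dose answers a somewhat different question. At Day 57, a patient with residual AK and a patient with a lingering reaction may look the same in the table.

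The omission also stands out within the SAP. Change from baseline or a shift table is planned for Skindex-16 (6.3.2.1), lesion count (6.3.2.5), Olsen grade (6.3.2.6), and vital signs and physical examination (6.4.5), but not for these signs.

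**Working it through.** The documents state no rate for these signs, so there is no figure to reproduce. Three checks follow.

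**1. What two visit percentages can identify.** Let b be the share with any sign of grade 1 or higher at Baseline, and d the share at a later visit in the same patients. The share newly positive lies between max(0, d − b) and min(d, 1 − b). The values of b and d below are illustrative.

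- b = 50%, d = 50%: from max(0, 0) = 0% to min(50%, 50%) = 50%.
- b = 50%, d = 85%: from 85% − 50% = 35% to min(85%, 50%) = 50%.

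So side-by-side columns bound the patient-level answer but do not give it. A patient who goes from grade 1 to grade 3 is positive at both visits, so the at-least-mild row does not register the worsening.

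**2. Who could carry a disease sign to Day 57.** Protocol 5.1.4 gives complete clearance with tirbanibulin of 44% and 68% in the two phase 3 trials. Protocol 5.2 gives 44% and 54% for the same trials, so the two sections disagree. With 420 patients:

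- (1 − 0.68) × 420 = 134
- (1 − 0.54) × 420 = 193
- (1 − 0.44) × 420 = 235

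That is 32-56% of patients, or 46-56% on the figures in Protocol 5.2 alone. These are patients with lesions left in the field, not patients with a miscounted sign.

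**3. Why the visit matters.** Let e be the share with a truly new or worsened sign, and q the chance that a Baseline sign persists. Assuming independence, the share counted is 1 − (1 − e)(1 − bq), which exceeds e by (1 − e) × bq. None of these rates is in the documents. The assumed values are e = 80% at Day 8 and 5% at Day 57, with bq from 0.10 × 0.5 = 0.05 to 0.50 × 1.0 = 0.50. That range stays below the 56% ceiling from check 2.

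| Visit | Assumed e | Counted, bq = 0.05 | Counted, bq = 0.50 | Excess over e |
|---|---|---|---|---|
| Day 8 | 80% | 1 − 0.20 × 0.95 = 81% | 1 − 0.20 × 0.50 = 90% | 1 to 10 points |
| Day 57 | 5% | 1 − 0.95 × 0.95 = 9.8% | 1 − 0.95 × 0.50 = 52.5% | 4.8 to 47.5 points |

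The contrast comes from the factor (1 − e). Where most patients have a true reaction, few are left to be counted on disease alone. The table shows direction only and does not estimate anything in this trial.

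**The case against.** The strongest reply is that Baseline is one of the summarized visits. The at-least-mild frequency, each sign and the composite all appear for Day 0 beside Day 8 and Day 57, and every sign is listed by patient. That stands: a group-level comparison with the pre-dose state is available. For the composite, the mean change equals the difference of the visit means in the same patients, so there the gap is mainly the spread and precision of the change. The phase 1 description in Protocol 5.1.4, of signs peaking "before returning to or close to baseline", is likewise a course over visits that the planned table could show. It does not strengthen the point.

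A reader might infer that untreated disease is being reported as a reaction to tirbanibulin. The documents do not support that. The field has been treated by Day 8, the table includes a pre-dose visit at which no drug reaction is possible, and SAP 6.4.6 attributes no sign to the drug. Nor do they say that lesional redness is scored; they leave it open.

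A reader might also conclude that the definition should be replaced by worsening from Day 0. That would bring its own bias. Treatment is meant to clear red, scaly lesions, so a drug-induced grade 1 erythema that replaces a disease grade 1 would count as no reaction, and the composite could fall despite a real reaction. The present inclusive count is the cautious one for safety and should remain.

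Finally, the analysis is descriptive and no decision rule depends on it. This limits the consequence, but a descriptive rate should still be able to describe incidence after treatment.

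**Conclusion.** The point holds as a gap in the planned displays. The by-visit tables cannot tell signs that are new or worse after treatment from pre-existing or residual AK, although the data to do so are collected. This rests on the text of SAP 2, SAP 6.4.6 and Protocol 11.4.1, and on the overlap between the disease and two of the six signs.

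The size is unknown because no baseline prevalence of the signs is given. The distortion is probably small at Day 8, within the Day 5-10 window in which Protocol 5.1.4 places the peak of erythema and scaling in phase 1, and larger at Day 57. The 32-56% with residual lesions is only the pool at risk; reading it as the number of patients wrongly counted would go beyond the documents. This is an inexpensive improvement to the SAP and does not invalidate the planned tables.

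**What to change.** Keep the by-visit tables and the at-least-mild count as they are. Add to SAP 6.4.6, for investigator-graded signs:

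- a shift table for each sign, Day 0 grade against Day 8, Day 57 and maximum post-baseline grade;
- the number and percentage of patients with a sign new or worse than on Day 0, per sign and overall;
- the change from Day 0 in the 0-18 composite at Day 8 and Day 57.

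Label these as supplementary to the by-visit definition. State that lesion clearance can lower a grade and so mask a reaction. State also that the maximum post-baseline grade rests on the investigator visits summarized (Day 8 and Day 57), because signs on Days 0-4 come from the patient diary and are summarized separately.

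The cost is SAP wording and a few tables from data already collected, with no change to visits or procedures.
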